3.2 Background

Bronchiolitis of infancy is a seasonal viral disease of the lower airways that most commonly causes feeding difficulties and respiratory distress and in severe cases causes a significant public health burden due to hospitalisation and mortality(1). It is the single most common reason for hospital admission of infants (children age<1yr). The youngest of these and those born prematurely are most often and most severely affected (1).

A recent study of Hospital Episode Statistics for England found 25,000 cases of bronchiolitis from each annual birth cohort (40.4 per 1000 (95% CI 38.5 to 42.3)) were admitted to hospital in their first year of life (2). Using PICANet data, the same study found just over 1000 of these infants were admitted with critical illness to English paediatric intensive care units (PICUs) each year (95% CI 1.3 to 1.6 per 1000 infants/yr) for mechanical ventilation (MV). This accounted for 12% of all admissions to PICUs. The infants' modal age was 1 month; the mean duration of PICU admission was 6.1 days (95% CI 5.4 to 6.7 days), and their case-fatality rate was 1.75%.

Despite advances in the provision of non-invasive modes of respiratory support, admissions to PICU and duration of MV for life-threatening bronchiolitis have remained static for the past 4 years (2). Excluding infants with rare congenital co-morbidities (mostly cardiac & neuromuscular anomalies), infants requiring MV for bronchiolitis do so for a mean of 4.8 days (SD 2.5d) (PICANet data, 2011-14).

Existing Research

In 2015 Jat & Chawla (3) found on pooled analysis of three small studies a significant reduction in length of PICU stay between endotracheal surfactant treated and control groups (mean difference (MD) -1.81d (95%CI -2.42 to -1.19) of critically ill infants with bronchiolitis who required MV. There were sustained improvements of arterial oxygenation (PaO₂) and carbon dioxide (PaCO₂) elimination (4-6). No adverse effects or complications were observed in the three studies. The authors of this systematic review and meta-analysis concluded that use of surfactant had favourable effects but that larger trials with adequate power were required to evaluate the effectiveness of surfactant therapy in critically ill infants with bronchiolitis who required MV.

IRAS 220853 Page 17 of 87

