11.3 Sample Size calculation

The study will be powered to detect a minimally clinically important difference of 18 hours (0.75 days) in the primary outcome variable of time of mechanical ventilation. Data are expected to be positively skewed, and will therefore be log-transformed, and resulting data back-transformed. The null hypothesis is that of no difference in time of MV between the two groups.

Data from Alder Hey Children's Hospital from an audit of 60 eligible infants admitted to PICU in the seasons 2012/3 and 2013/4 showed a mean (SD) duration of ventilation of 4.83 (2.5) days (PICANet data, 2011-14). Parameters for sample size estimation are therefore as follows:

```
E(Y_1) = 4.83 \text{ and } SD(Y_1) = 2.5 E(Y_2) = 4.08 \text{ and } SD(Y_2) = 2.5 \delta = E(Y_2)/E(Y_1) = 0.845 giving coefficients of variation: \kappa_1 = SD(Y_1)/E(Y_1) = 2.5/4.83 = 0.518 \kappa_2 = SD(Y_2)/E(Y_2) = 2.5/4.08 = 0.613
```

Using the formula of Wolfe and Carlin (1999) with r = 1 for equal allocation and a two-sided alphalevel of 0.05, sample size estimations are 100 per group for 80% power and 134 per group for 90% power.

Taking the sample size of 134 and allowing for 5% dropout requires 142 patients will be recruited to each group, giving a total of 284 participants overall.

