# 5. Statement of Compliance

This Statistical Analysis Plan (SAP) provides a detailed and comprehensive description of the preplanned final analyses for the study "BESS". The planned statistical analyses described within this document are compliant with those specified in brief within the BESS protocol v3.0 (31/07/2019). These analyses will be performed by the trial statistician.

This study is carried out in accordance with the World Medical Association Declaration of Helsinki (1964) and the Tokyo (1975), Venice (1983), Hong Kong (1989) and South Africa (1996) amendments and will be conducted in compliance with the protocol, Liverpool Clinical Trials Centre (LCTC) Clinical Trials Unit (CTU) Standard Operating Procedures (SOPs) and EU Directive 2001/20/EC, transposed into UK law as the UK Statutory Instrument 2004 No 1031: Medicines for Human Use (Clinical Trials) Regulations 2004.

This study is a clinical trial of a medicinal product and is registered on the EudraCT database. This SAP has been developed to support the posting of results on the EudraCT system. This is a regulatory requirement which should be fulfilled within 6 months after the end of the study as defined within the clinical trial protocol. The results of the final analysis described within this SAP will be contained within a statistical analysis report. This report will be used as the basis of the primary research publications according to the study publication plan.

All analyses are performed with standard statistical software (SAS v9.4 or later) with the exception of the joint modelling analysis which will be performed using the JoineR package [5] package in R. The finalised analysis datasets, programs and outputs will be archived following Good Clinical Practice (GCP) guidelines and SOP GE012 Archiving procedures. The testing and validation of the statistical analysis programs will be performed following SOP ST001.

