#### 17.2. Demographic and Other Baseline Characteristics

Descriptive statistics will be presented split by treatment group and overall. Categorical data will be summarised by frequencies and percentages to one decimal place. Continuous data will be summarised to one decimal place by mean (standard deviation), median (interquartile range) and

#### Form prepared: 16/04/2024 v2.0 for BESS Page 14 of 30

range, irrespective of distribution. No formal statistical testing will be undertaken, but the clinical significance of any imbalance will be noted.

Baseline variables to be included:

- Whether infant premature or term-born
- Age/corrected age at randomisation
- Sex
- Weight
- Whether infant intubated upon arrival at PICU
- Whether infant on oxygen supplementation upon arrival at PICU
- Time on MV prior to randomisation
- Underlying viral/bacterial infection

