# 17.4.1.2. Analysis

Descriptive statistics will be presented split by treatment and overall for the time from randomisation to final successful extubation (before the data is transformed) and time off MV due to failed extubation. The summaries will be presented as median and interquartile range as the data is likely to be skewed.

A comparison of group means will be conducted using a two-sample t-test on the log transformed data (the log transformation will be done using natural logarithms). The between group difference of the log transformed data will then be back transformed by taking the exponent to give the geometric mean difference and the corresponding 95% confidence interval.

A linear mixed effects model will also be fitted on the log transformed data, using ANCOVA to test for a difference between groups with adjustment for the stratification factor of time on ventilation prior to randomisation (<24h and  $\geq$ 24h), sex and adjusted age at enrolment as a fixed effects and site as a random effect (random intercept only). The exponentiated between-group difference and corresponding 95% confidence interval will be reported.

The approach to the primary outcome analysis will be a compete case analysis and will only include those participants for which the primary endpoint has been observed. If there are any participants who have not recorded a successful extubation at the point at which they were last followed up (e.g. consent for follow up has been withdrawn) then sensitivity analysis will be conducted including these participants to assess the robustness of the primary outcome analysis.

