## 18. Missing data and withdrawals

Missing data will be quantified for all outcomes presented in the final analysis report. Where known, reasons for missingness will be given.

Withdrawals from trial will be summarised and presented as line listings detailing:

- 1. Site
- 2. Time from randomisation to withdrawal
- 3. Decision to withdraw participant made by:
  - a. Clinician
  - b. Parent/person with parental responsibility
  - c. Both clinician and parent/person with parental responsibility
- 4. Reason for withdrawal:
  - a. Death
  - b. Lost to follow-up
  - c. Transfer to non-participating site
  - d. Withdrawal of consent for follow-up
  - e. Other (specify)

Every effort will be made to collect follow-up data even in the event of participants discontinuing the trial intervention. In the case of withdrawals from study, available data will still be included using an intent-to-treat approach.

#### 19. Additional analyses Additional analysis 1

A sensitivity analysis of the primary analysis will be done to assess the robustness of the primary analysis. This will be done using a Cox proportional hazards model and will allow the censoring of patients who do not observe the primary endpoint of successful extubation. The start-point and end point for patients having the event of successful extubation will be the same as those defined in section 17.4.1.1. For patients who do not have a successful extubation recorded these will be censored at the last date and time (OAODATXD) an observation is recorded on the Observations and Outcomes CRF. The cox proportional hazards model will include the allocated treatment and time on ventilation prior to randomisation as covariates.

#### Additional analysis 2

A subgroup analysis of the primary outcome will be undertaken, This was based on a recommendation from the Trial Steering Committee who met on the 20th February 2024.

The subgroup analysis will examine the primary outcome stratified by whether the baby was born prematurely or not and will include an interaction term between treatment and prematurity in the linear mixed effect model described in 18.4.1.2.

Results will be presented from the model with the interaction result alongside.

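### SAP section 19 adds a treatment-by-prematurity interaction to a mixed model that has no prematurity term and never names the main effect; fitted literally, the interaction test would absorb prematurity's own effect on ventilation time

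*SAP*

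**What the plan says.** SAP section 17.4.1.2 describes a mixed model for log ventilation time. It contains treatment, the prior-ventilation stratum (under 24 hours, or 24 hours and over), "sex and adjusted age at enrolment as a fixed effects and site as a random effect (random intercept only". Whether the infant was born preterm is not in the list.

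SAP section 19, Additional analysis 2, was added in version 2.0 on the recommendation of the Trial Steering Committee. It says "The subgroup analysis will examine the primary outcome stratified by whether the baby was born prematurely or not", and that the analysis "will include an interaction term between treatment and prematurity in the linear mixed effect model described in 18.4.1.2". No section numbered 18.4.1.2 exists in the body. The number follows the SAP's contents list, which runs one ahead of the body, so 17.4.1.2 is meant.

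Prematurity is available: SAP section 17.2 lists "Whether infant premature or term-born" among the baseline variables. On prognosis, protocol section 3.2 says of infants with bronchiolitis: "The youngest of these and those born prematurely are most often and most severely affected".

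**The concern.** An interaction measures a difference in treatment effect only if the model also contains the main effects of both variables. Neither section 17.4.1.2 nor section 19 names a main effect of prematurity. Elsewhere this SAP spells out its covariates (the SF-ratio model, the LRSQ model, the Cox model), so a programmer could reasonably add the one named term to the listed model and stop there.

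In that model, prematurity's own effect on ventilation time has nowhere to go except the interaction. Adjusted age does not take its place: a 12-week-old born 12 weeks early has the same adjusted age as a term newborn.

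This is the only planned subgroup analysis of the primary outcome. A prognostic difference could be reported as surfactant working differently in preterm infants. Section 21 of the SAP has a second statistician re-program the primary and safety analyses, and it does not clearly extend to this one.

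**Working it through.** **1. The plan's own figures.** Protocol section 11.3 gives a control mean of 4.83 days, a treated mean of 4.08 and an SD of 2.5 in both arms, so the coefficients of variation are 0.518 and 0.613.

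- Log variances: ln(1 + 0.518²) = 0.237 and ln(1 + 0.613²) = 0.319.
- Log difference: ln(0.845) − ½(0.319 − 0.237) = −0.2095.
- n per group = (z_α/2 + z_β)² × (0.237 + 0.319) / 0.2095², which gives 99.5 → 100 for 80% power and 133.2 → 134 for 90%. Then 134/0.95 → 142 per group, 284 in total.

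The stated sizes reproduce. The calculations below use 134 per arm (268 analysed) and a log SD of 0.487 (control, √0.237) or 0.527 (average of the two variances).

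**2. What the literal model estimates.** Let log time = μ + θT + βP + error, with no true interaction, P = 1 for preterm and p the preterm share. Fit T and the 0/1 product T×P without P:

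- the placebo arm has one mean for term and preterm infants, μ + pβ;
- the T×P coefficient estimates treated preterm minus treated term, which is β (the truth for an interaction is 0);
- the T coefficient estimates θ − pβ instead of θ.

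For ventilation 25% longer in preterm infants, β = ln 1.25 = 0.223. The T coefficient moves from −0.2095 to −0.2095 − 0.2 × 0.223 = −0.254 (20% preterm) or −0.2095 − 0.4 × 0.223 = −0.299 (40%). Simulation gave −0.251 and −0.296.

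**3. Approximate false-positive rate.** SE = 0.527 × √[1/(134p) + 1/(134(1 − p))], which is 0.114 at p = 0.2 and 0.093 at p = 0.4. With β = 0.223 the ratios β/SE are 1.96 and 2.40, so a 5% test rejects in about 50% and 67% of trials. This is slightly high, because it ignores the part of β that adjusted age picks up and the extra residual variance in the placebo arm.

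**4. Simulation.** There is no true interaction. N = 268, log SD 0.527, 2,500 runs per cell, with prior ventilation, sex, adjusted age and site in the model (site as fixed indicators). Interaction rejected at 5%, for 20 / 30 / 40% preterm:

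| Longer MV in preterm | No prematurity main effect | With main effect |
|---|---|---|
| 0% | 5.3 / 4.9 / 4.6% | 5.6 / 4.9 / 4.9% |
| 10% (0.095 log) | 12.8 / 14.6 / 16.6% | 4.7 / 4.8 / 4.8% |
| 25% (0.223 log) | 46.0 / 55.8 / 62.4% | 4.8 / 4.4 / 5.5% |

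Two further sets of runs used effects of 0.1 / 0.2 / 0.3 log units (11 / 22 / 35% longer) and 20–40% preterm. One, with log SD 0.487 and no site effects, gave 12–14% / 35–43% / 63–74%. The other gave 13–18% / 41–53% / 73–87%. Together they span about 12–87%. With the main effect included, rejection was about 5%.

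The ends of that range are not sharp. With SD 0.527 and adjusted age correlated with prematurity, the lower end was 10%. With SD 0.487 and adjusted age independent of it, the upper end was 92%.

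**5. Coding.** Step 2 assumes a numeric product. If treatment and prematurity are both class variables, treatment plus the cross term spans all four cells. The default test of the cross term is then a 2-df test of prematurity within each arm. In the simulation of step 4 it rejected in 66–85% of runs at a 25% effect, so it is not an interaction test either.

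**6. Precision in the adjusted primary model.** Adding P removes a share p(1 − p)β² / [σ² + p(1 − p)β²] of the residual variance. With σ² = 0.278:

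- p = 0.2, β = 0.1: 0.0016/0.2796 = 0.6%;
- p = 0.4, β = 0.3: 0.0216/0.2996 = 7.2%.

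The simulation at SD 0.487 gave about 0.5–6%.

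**The case against.** The strongest reply is that section 19 does not exclude a main effect. It does not say that the interaction is the sole addition, and it speaks of the outcome being stratified by prematurity. By ordinary convention an interaction comes with both main effects. This stands. A reader might infer that the SAP specifies a faulty model, and the text does not support that. It leaves the model open, and stratification could equally mean a model term, separate models or separate presentation.

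The shared placebo mean also depends on numeric coding. The SAP uses "standard statistical software (SAS v9.4 or later"; under class coding the four cell means are all free and correct within-stratum contrasts can be recovered. This also stands, but the default test of the cross term would still not be the one wanted.

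Nor do the documents show that prematurity lengthens ventilation in this population. The remark in protocol section 3.2 concerns infants with bronchiolitis in general, whereas every infant here is already ventilated. It makes a prognostic effect plausible and gives no size.

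Finally, a reader might infer that leaving prematurity out of 17.4.1.2 biases the primary result. It does not: omitting a baseline covariate leaves the randomised comparison unbiased, and protocol section 11.5 asks only for the stratification factors.

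**Conclusion.** The subgroup model in section 19 is under-specified. If it is fitted literally, its interaction test is invalid whenever prematurity affects ventilation time. The false-positive rate is then roughly 12–87% instead of 5%, for an assumed 20–40% preterm share and an assumed effect of 0.1–0.3 log units. It stays near 5% if prematurity has no effect, and returns to about 5% once the main effect is in the model. These are conditional rates for one reading of the text, not the error rate of the analysis that will necessarily be run.

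The unadjusted t-test, the adjusted treatment estimate in 17.4.1.2 and the safety results are unaffected. The wrong section number is a clerical slip with an unambiguous target.

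**What to change.** In SAP section 19, Additional analysis 2, state that the model contains treatment, prematurity (born preterm, yes or no) and treatment × prematurity, together with the existing covariates and random site intercept of 17.4.1.2. Ask for the ratio of geometric means with its 95% CI in term and in preterm infants, and for the 1-df interaction test. Replace 18.4.1.2 with 17.4.1.2.

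As a low-cost improvement, also add prematurity as a fixed effect in the 17.4.1.2 mixed model. The gain is small (about 0.5–7% lower residual variance under the same assumptions) and the subgroup correction does not depend on it.

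The cost is one or two sentences in the SAP and one degree of freedom in the primary mixed model. No new data are needed. The change should be made before the allocation codes are released to the statistical team.

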10.2.3 Notification of deaths

There is an overall likelihood of death in all cases of severe bronchiolitis of 1-2%. All deaths that occur during the protocol-specified AE reporting period, regardless of relationship to study drug, must be recorded. All deaths should be reported on a "Serious Adverse Event CRF" and returned to the CTRC within 24 hours.

Death should be considered an outcome and not a distinct event. The event or condition that caused or contributed to the fatal outcome should be recorded as the single medical concept on the appropriate CRF; e.g. death following pneumothorax, here pneumothorax is the event. Generally, only one such event should be reported. The term "sudden death" should only be used for the occurrence of an abrupt and unexpected death due to presumed cardiac causes in a participant with or without pre-existing heart disease, within 1 hour of the onset of acute symptoms or, in the case of an unwitnessed death, within 24 hours after the participant was last seen alive and stable. If the cause of death is unknown and cannot be ascertained at the time of reporting, "unexplained death" should be recorded on the appropriate CRF. If the cause of death subsequently becomes available (e.g. after post-mortem examination), "unexplained death" should be replaced by the established cause of death.

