#### 17. Efficacy Evaluations

#### 17.1. Data Sets Analysed

The principle of intention-to-treat, as far as practically possible, will be the main strategy of the analysis adopted for the primary outcome and all secondary outcomes. These analyses will be conducted on all randomised participants, in the group to which they were randomised, and for whom the outcome(s) of interest have been observed/measured. No imputations will be made.

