# 17.4.1.1. Derivation

The duration of mechanical extubation will be calculated by identifying the date and time (OAODATXD) associated with final extubation as indicated by OAOOUTCC = "Successful" on the Observations and Outcomes CRF. The difference between the date/time of randomisation taken from the Almac randomisation log and the date/time of successful extubation will be calculated in hours and transformed using natural logarithms.

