#### 17.4.4.2. Analysis

Summary statistics will be presented in a table for each time point (0 hours, 12, hours, 24 hours, 36 hours, 48 hours then every 24 hours while still on MV if the number of observations is  $\geq$  5 overall at the time points following 48 hours) detailing the mean and standard deviation of each of the derived measures (VI, OI and OSI) for each treatment arm and overall.

The relationship between longitudinal data for VI, OI and OSI and the event of successful extubation will be examined visually by plotting mean profile plots of longitudinal data separated by treatment group and by the time at which the final observation was observed and comparing this to the overall mean profile plot separated by treatment group.

Infants will have differing amounts of follow-up data for the outcomes VI, OI and OSI as these are recorded while on MV only. More specifically, infants who are successfully extubated earlier (and therefore completing follow-up earlier) will have less follow-up data than infants with a later successful extubation time. This will be addressed in analyses of both the longitudinal measurements (VI, OI and OSI) and the time to event outcome (time to successful extubation) using joint modelling. Joint modelling will account for the potentially informative drop-out in longitudinal measures due to successful extubation. For each measure the treatment effect will be reported together with a 95% CI and a p-value.

For the SF ratio, a repeated measures random effects model will be fitted. The dependent variable will be post baseline (0 hours) SF ratio measurements. Covariates will be: SF ratio at baseline (0 hours), treatment arm, time (fitted as a continuous variable), and the stratification factor of time on ventilation prior to randomisation (<24h and  $\geq$ 24h). Centre will be fitted as a random intercept. The treatment effect (estimated mean difference in SF ratio) will be reported together with a 95% CI and a p-value.

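### Death before successful extubation is dropped from both primary comparisons and only censored in the one specified sensitivity model, so no analysis of the primary outcome counts it as a bad result

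*SAP*

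**What the plan says.** SAP 17.4.1.1 measures the endpoint from randomisation to the date and time of "final extubation as indicated by OAOOUTCC" equal to Successful, then takes logs. It gives no rule for an infant who dies first. SAP 17.4.1.2 compares the arms by a two-sample t-test and a linear mixed model, and says the approach "will be a compete case analysis and will only include those participants for which the primary endpoint has been observed". SAP 17.1 limits intention-to-treat in the same way for every outcome, to infants "for whom the outcome(s) of interest have been observed/measured. No imputations will be made". The prematurity subgroup in SAP 19 reuses the mixed model.

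If an infant has no successful extubation recorded at last follow-up, SAP 17.4.1.2 says "then sensitivity analysis will be conducted including these participants to assess the robustness of the primary outcome analysis". Its only example is withdrawn consent. The one such analysis specified is a Cox model (SAP 19, Additional analysis 1) that "will allow the censoring of patients who do not observe the primary endpoint of successful extubation", at the last date and time held in OAODATXD.

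Death is foreseen elsewhere:

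- Protocol 10.2.3 states: "There is an overall likelihood of death in all cases of severe bronchiolitis of 1-2" per cent. Protocol 3.2 gives a case-fatality rate of 1.75% for intensive-care admissions.
- SAP 17.4.8.1 has a rule for death in the length-of-stay outcomes, and SAP 18 lists death as a reason for withdrawal.
- SAP 17.5.5 and 17.5.6 compare deaths by allocated arm as safety outcomes.

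**The concern.** Dying on the ventilator is a post-randomisation event that treatment could affect. The primary comparisons condition on its not having happened, so for infants who die the treatment effect is left undefined. The Cox model keeps these infants in the risk set until censoring. Read as an analysis of time to extubation, it then treats them as if they would have gone on to be extubated at the survivors' rate. Read as a cause-specific extubation rate it is a recognised quantity, but it still does not count the death against the arm.

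At stake is whether an imbalance in deaths could pass unnoticed through the headline result. If an arm lost infants who were heading for long ventilation, its survivors would show shorter durations for a reason that is not benefit.

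**Working it through.** **Inputs from Protocol 11.3.** Mean 4.83 v 4.08 days, SD 2.5 in both arms, two-sided alpha 0.05, 1:1 allocation, 142 per arm.

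**The plan's own figure.** With s² = ln(1 + κ²):
- s₁² = ln(1 + 0.518²) = 0.237 and s₂² = ln(1 + 0.613²) = 0.319.
- d = ln(4.08/4.83) − (0.319 − 0.237)/2 = −0.209, a design ratio of geometric means of 0.811.
- n = (z_α/2 + z_power)²(s₁² + s₂²)/d² = 99.5 (80% power) and 133.2 (90% power), so 100 and 134.
- 134/0.95 rounds up to 142 per arm, 284 in total. The sample size reproduces.

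**Expected deaths among 284.** 1% gives 2.8, 1.75% gives 5.0 and 2% gives 5.7: about 3 to 6 over both arms.

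**Upper bound on the shift.** Suppose 5 excess surfactant deaths are the 5 longest stayers of 142 (3.5%).
- Removing the top 3.5% of a normal distribution moves its mean by −φ(1.81)/0.965 = −0.0805 SD.
- On the log scale this is −0.0805 × 0.487 = −0.039, a ratio of 0.962.
- The placebo geometric mean is 4.83/√1.268 = 4.29 days = 102.9 h, so the shift is 102.9 × 0.038 ≈ 4.0 h.
- The standard error is about 0.487 × √(2/142) = 0.058, so z is about −0.7. On the same calculation about 20 excess deaths (14% of the arm) would be needed for this bias alone to reach significance (z = −2.19).

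**Simulation with fixed deaths.** Log-normal durations, 142 per arm, no effect on ventilation, complete-case t-test on logs, 3,000 to 5,000 trials per scenario. Ranges come from repeated independent runs. The nominal one-sided rate is 2.5%.

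| Deaths, surfactant v placebo | Who dies | Ratio | False finding for surfactant |
|---|---|---|---|
| none | – | 1.00 | 2.8% |
| 2 v 1 | longest-stay fifth | 0.996 | 2.9% |
| 3 v 2 | longest-stay fifth | 0.995 | 3.2% |
| 4 v 1 | longest-stay fifth | 0.985 | 4.4–4.5% |
| 5 v 0 | longest-stay fifth | 0.974–0.976 | 6.1–7.1% |
| 5 v 0 | upper half | 0.986 | 4.1% |
| 5 v 0 | at random | 0.999 | 2.4% |

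For 5 v 0 from the longest-stay fifth, the other analyses behave as follows:
- Cox with deaths censored: hazard ratio 1.02–1.03 (above 1 favours surfactant), false finding 4.0%.
- Deaths kept as never extubated: hazard ratio 0.91, so the harm shows.
- Worst-rank comparison: false finding 1.6–1.9%.

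**Dependence on who dies.** Assumed mortality is 1.75% on placebo and 5.25% on surfactant, which is 2.5 v 7.5 deaths. That is an excess of 5, but about 10 deaths in all, above the 3 to 6 expected.

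| Link between death and stay | Complete-case ratio | False finding | Cox hazard ratio, deaths censored |
|---|---|---|---|
| Longest stayers die | 0.966 | 11.5% | 1.055 |
| Moderate link to longer stay | 0.983 | 4.8% | 1.011 |
| Unrelated | 1.001 | 2.2% | 0.985 |
| Linked to shorter stay | 1.016 | 1.3% | 0.973 |

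The never-extubated analysis gave a hazard ratio below 1 in every excess-death scenario.

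**Would the safety comparison flag it?** For 5 v 0, two-sided Fisher p = 2 × (142·141·140·139·138)/(284·283·282·281·280) = 2 × 0.0302 = 0.06.

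**The case against.** A reader might infer that deaths caused by surfactant would necessarily make ventilation look shorter, and that the Cox model would repeat the error. The documents do not support either. Nothing in them says that infants who die would have had the longest ventilation, and the administration reactions listed in Protocol 3.4.2 (tube blockage, desaturation, bradycardia) are acute. With death unrelated to stay the complete-case ratio remains at 1.00. With death linked to shorter stay it moves against surfactant. The Cox hazard ratio follows the same condition: slightly above 1 only when the longer stayers die, and below 1 otherwise.

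Three further points stand:

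- A split of 5 v 0 is a corner case. Under equal mortality, five deaths fall that way against surfactant with probability 0.5⁵ = 3.1%. The exclusions in Protocol 6.2 (major anomalies, neuromuscular disease, ECMO or oscillation, futility) may also bring mortality below the quoted rates.
- Deaths are not hidden. They are compared by arm with a relative risk (SAP 17.5.5 and 17.5.6), and the CONSORT diagram gives reasons for exclusion from the primary analysis (SAP 14.1).
- SAP 17.1 openly qualifies intention-to-treat as applying as far as practicable.

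What these points do not answer is that a separate safety comparison neither corrects the primary estimate nor, at p = 0.06 for 5 v 0, reliably flags the imbalance.

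**Conclusion.** The gap is real and should be fixed, but it does not invalidate the primary analysis. Infants who die before a successful extubation are excluded from both primary comparisons and censored in the only specified check, so death cannot count against an arm anywhere in the analysis of the primary outcome.

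A lean towards benefit is possible, not automatic. It needs both an excess of deaths on surfactant and deaths concentrated among would-be long stayers. Even then, five excess deaths shift the result by at most about 4 hours. Where deaths are few and nearly balanced, the distortion is negligible. Where death is unrelated to stay, the failing is silence about harm, not false benefit.

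The figures rest on the protocol's log-normal planning inputs. The numbers of deaths by arm and their link to stay are assumptions. The reading also assumes that an infant who dies on the ventilator has no extubation coded Successful.

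**What to change.** In SAP 19, before unblinding:

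1. Name death before successful extubation as a competing event for the primary outcome.
2. Pre-specify one death-inclusive sensitivity analysis on all randomised infants. Either report the cumulative incidence of extubation alive by arm, with a Fine-Gray model that keeps deaths as never extubated, or use a worst-rank comparison. One is enough. Worst rank answers a somewhat different question from the ratio of geometric means, and the text should say so.
3. Keep the Cox model, described as estimating the cause-specific extubation rate.
4. Print the number of deaths before extubation by arm beside the primary result.
5. Confirm the censoring variable. SAP 17.4.1.1 uses OAODATXD for the extubation date and time, so it may be blank for infants never extubated. SAP 17.4.2.1 uses OAODATCD for the date and time of an observation.

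The cost is a paragraph in the SAP, a few lines of code and one more sensitivity result to report. Date of death is already collected (SAP 17.4.8.1).
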